### Safety

- Development of vulval intraepithelial neoplasia or vulval squamous cell carcinoma at 24 months.
- Targeted adverse events e.g. stinging, skin thinning measured by patient reported symptoms and clinical examination from randomisation over 24 months.

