## 1.2 Current management of LS

Treatment goals are to control symptoms, prevent scarring and reduce the risk of cancer. First-line therapy with a superpotent topical corticosteroid (TCS) applied daily for three months, combined with a soap substitute and barrier emollient to protect from irritants [14] achieves normalisation of skin colour/texture and resolution of symptoms in 70% patients [7]. However, LS is a relapsing-remitting condition and evidence to inform maintenance of remission/prevention of progression is poor. In many girls, the disease remits at puberty, but this cannot be assumed, and some studies describe a more chronic course where resolution does not always occur and continued treatment is necessary [15, 16]. A critically appraised topic has shown that 37% of girls have symptoms that persist past the first 3 months of treatment, 67% who were in remission recur after 1 year and 55% recur after 4 years [17].

It is important to note that LS can also affect boys and men, but there are differences in the management of male LS as circumcision is believed to be curative and long-term maintenance is usually not required. This protocol, therefore, is only in reference to women and girls with vulval LS.

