#### Screening for eligibility criteria

Once patients (identified through either PICs, self-referral or secondary care centres) confirm their expression of interest, they will be invited by site team to their first, screening/baseline visit. At this visit, the trial will be discussed in more detail and, if agreed, informed consent will be taken.

Following informed consent (section 7.9), eligibility will be confirmed by a site investigator, a medically qualified doctor, and baseline data will be collected. A physical investigation will be conducted to confirm diagnosis. Patients will be asked to confirm that they are symptom-free. Other eligibility criteria will be confirmed from medical notes or discussion. If the patient meets all eligibility criteria, they will be randomised to the trial treatment at which point the participant trial unique number will be allocated.

Those who do not meet the trial eligibility criteria, or do not wish to participate in the trial, not be randomised and will be excluded from the trial.

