### Baseline

#### Visit 1

(at baseline)

- Informed consent
- Eligibility check and confirmation
- Contact details
- Collection of baseline data:
  - Concomitant medication (relevant to condition) and relevant medical history
  - Demographic information
  - Clinician global severity assessment
  - Scarring assessment (VASS, clinical examination)
  - Vulval development and scarring (in adolescents and children)
  - Condition specific QoL (VQLI or CDQLI)
  - Health related QoL assessed by EQ-5D-5L in adolescents/adults and CHU-9D in children
  - Bespoke resource use questionnaire and healthcare questionnaire
- Clinical photographs, or clinical diagram if consent for photographs not taken
- Randomisation

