#### Clinical photographs

Photographs will be taken at baseline for patients who consent to this, to assess scarring. Photographs will not be a mandatory requirement as some patients are hesitant due to the intimate nature of LS. Parents of children with LS are less likely to consent to photographs. Photographs taken up to 1 month prior to baseline appointment can be accepted, if the patient had no active disease during this period. If a photograph is not taken, clinicians will be asked to document a detailed clinical diagram (using a predefined schematic diagram) for comparison. Images taken at the baseline will remain in participant's medical notes and will not be sent to NCTU. Subsequent clinical examinations will assess changes against the baseline photo/diagram. Blinded assessments of scarring (or failure of normal anatomical development as appropriate) will be assessed at 12 and 24 months comparing to baseline clinical photographs.

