## 8.7 Trial assessments\*

Table 7. Data collection timepoints

Trial assessment	Source	Timepoint and visit number					
		Screening/baseline Visit 1	3 month Visit 2	6 month Visit 3	12 month Visit 4	18 month Visit 5	24 month Visit 6
Confirmation of eligibility	Medical notes/clinician/participant	X					
Consent	Participant	X					
Randomisation	Participant	X					
Medical history	Participant/medical notes	X					
Demographic information	Participant/medical notes	X					
Concomitant medication (relevant to condition only)	Participant	X	X	X	X	X	X
Number of flares and time to 1st flare	Participant	Starting 2 weeks from randomisation, every 2 weeks for 12 months					
Progression of scarring via photograph (optional), VASS and examination	Clinician	X **			X €		X €
Vulval development and scarring (adolescents and children)	X	X	X	X	X	X	X
Clinical global severity assessment	Clinician	X	X	X	X μ	X	X μ
Condition specific Quality of Life (VQLI or CDLQI)	Participant	X	X	X	X	X	X
Health related quality of life (generic utility instrument) (EQ-5D-5L in adolescents/adults or CHU-9D in children)	Participant	X	X	X	X	X	X
Sexual function using Female Sexual Function Index (adults only)	Participant				X		X
Acceptability of treatment	Participant				X		X
Adherence to treatment	Participant		X	X	X	X	X
Resource use (bespoke and healthcare)	Participant	X	X	X	X	X	X
VIN or vulval SCC	Clinician						X
Adverse effects of therapy	Participant, Clinician		X	X	X	X	X
Change/cessation of therapy	Participant		X	X	X	X	X
* Definition of age groups for purpose of assessments is described in section 4.4		° At 12 and 24 months assessed by blinded assessor					
** Assessed by photographs (if consented) or clinical assessment diagram		μ At 12 and 24 months assessed by treating clinician and blinded assessor					
€ Clinical assessment comparing to baseline photographs (if consent given for photographs) or to baseline clinical assessment diagram if consent for photographs not obtained							

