## 11 ADVERSE EVENTS

An adverse event is any unfavourable and unintended sign, symptom, syndrome or illness that develops or worsens during the period of observation in the study.

An AE includes:

1. Exacerbation of a pre-existing illness.
2. Increase in frequency or intensity of a pre-existing episodic event or condition.
3. Condition detected or diagnosed after medicinal product administration even though it may have been present prior to the start of the trial.
4. Continuous persistent disease or symptoms present at baseline that worsen following the start of the trial.

The interventions being evaluated in this trial are treatments that are widely available within the NHS and used in standard care for lichen sclerosus. Given the well-known safety profile of the interventions, we will adopt a targeted approach to AE reporting.

Reporting and follow-up of these targeted participant and investigator-reported complications associated with the intervention delivery will be recorded in trial e-CRFs in a structured format and do not need to be reported to the Research Ethics Committee (REC).

An AE does not include:

1. Medical or surgical procedure (e.g., surgery, endoscopy, tooth extraction, transfusion); but the condition that leads to the procedure is an AE.
2. Pre-existing disease or conditions present or detected at the start of the trial that did not worsen.
3. Situations where an untoward medical occurrence has not occurred (e.g. hospitalisations for cosmetic elective surgery, social and / or convenience admissions).
4. Disease or disorder being studied or sign or symptom associated with the disease or disorder unless more severe than expected for the participant's condition.
5. Overdose of concurrent medication without any signs or symptoms.

Although all AEs should be recorded in the medical notes, in accordance with GCP, only those AEs which are directly referred to in the e-CRF will be collected for this trial. However, where any AE event meets the criteria of an SAE (see section 11.2), it will require reporting on a SAE form by the PI or delegate.

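### Chronic steroid skin signs are safety outcomes with no dedicated baseline record, so carried-over damage may be counted in both arms and dilute the contrast between strategies

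*Protocol*

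**What the plan says.** Secondary objective 3 is the safety of potent and superpotent TCS over 24 months. Under Safety, section 4.4 gives the outcome as "Targeted adverse events e.g. stinging, skin thinning measured by patient reported symptoms and clinical examination from randomisation over 24 months". Section 11.4 lists the targeted events, which include thinning, wrinkling, striae and telangiectasia.

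In Table 7 (section 8.7) the row "Adverse effects of therapy" is marked at 3, 6, 12, 18 and 24 months and left blank at screening/baseline. The Visit 1 list in section 8.1 contains scarring with VASS and clinical examination, vulval development in younger participants, global severity, relevant medical history, and a photograph or diagram. It has no item for steroid skin damage. The purpose of the baseline procedures is stated elsewhere: "A physical investigation will be conducted to confirm diagnosis" (section 7.2, screening for eligibility) and "Photographs will be taken at baseline for patients who consent to this, to assess scarring" (section 8.1). Sections 1.5 and 8.5 place the monitoring of thinning and telangiectasia at follow-up or unscheduled visits.

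Section 11 opens by confining adverse events to what arises or gets worse during observation. It then lists among adverse events: "Condition detected or diagnosed after medicinal product administration even though it may have been present prior to the start of the trial". Among the things that are not adverse events it lists: "Pre-existing disease or conditions present or detected at the start of the trial that did not worsen". Section 10.6 plans descriptive counts and percentages by group.

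**The concern.** Whether twice-weekly maintenance adds local skin damage is a central safety question here, and section 2.6 itself notes how little evidence there is to quantify such harms. Thinning, striae and telangiectasia are chronic signs. A sign seen at month 3 may be new or may have been there at entry.

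Some entrants probably carry such signs. Section 1.2 describes usual treatment as "First-line therapy with a superpotent topical corticosteroid (TCS) applied daily for three months", and section 7.4.1 requires controlled disease at entry. Prior exposure is therefore likely, although it is an inference and not an entry criterion.

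Section 11's rules depend on knowing what was present at the start, and the schedule does not ask anyone to write that down for these signs. Carried-over damage may then be entered as an adverse event at some sites and not at others. In both arms this would raise the reported rates and bring them closer together in relative terms, which could make proactive treatment look safer relative to reactive treatment than it is. A SAP cannot recover a baseline that was never collected.

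**Working it through.** **1. Is there a baseline record?**
- The outcome is defined by examination (sections 4.4 and 11.4).
- First scheduled collection is month 3 (Table 7). Visit 1 has no matching item (section 8.1).
- What exists at baseline is aimed at diagnosis and scarring. Photographs are optional and stay in the medical notes; a diagram replaces them where consent is withheld.
- By contrast, scarring has an explicit baseline comparator in sections 4.4 and 8.1 and Table 7.

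**2. Do the adverse event rules settle the matter?** Take thinning first noted at month 3, with its state at entry unknown. The opening definition and the exclusion item leave it out if it was present and has not worsened. The inclusion item counts it even if it was present before. The site can choose between them only by knowing the state at entry.

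**3. Size of the effect.** The protocol gives no rate, prevalence or power for skin damage, so there is no figure of its own to reproduce on this point. Its one power figure (320 analysed, 400 randomised) concerns flares and is unaffected. The following values are assumptions:
- true incidence of new damage: 10% proactive, 5% reactive;
- p0, the proportion with signs already present at entry: 10%, 20% or 30%, equal in both arms in expectation through randomisation;
- every pre-existing case is recorded as an adverse event, which is the worst case.

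Observed proportion = p0 + (1 − p0) × incidence. For p0 = 20%: proactive 0.20 + 0.80 × 0.10 = 0.28; reactive 0.20 + 0.80 × 0.05 = 0.24.

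| p0 | Proactive | Reactive | Risk difference (points) | Risk ratio |
|---|---|---|---|---|
| 0% | 10.0% | 5.0% | 5.0 | 2.00 |
| 10% | 19.0% | 14.5% | 4.5 | 1.31 |
| 20% | 28.0% | 24.0% | 4.0 | 1.17 |
| 30% | 37.0% | 33.5% | 3.5 | 1.10 |

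The risk difference shrinks only by the factor (1 − p0). The ratio shrinks much more, because the same number of old cases is added to both arms.

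**4. Precision.** Section 10.6 plans no test, so power serves only as a gauge. With 400/2 = 200 per arm, power = Φ[(|Δ| − 1.96 × SE0)/SE1], where SE0 is the pooled and SE1 the unpooled standard error.
- No carry-over, 5% v 10%: SE0 = 0.0263, SE1 = 0.0262, power 48%.
- p0 = 20%, no baseline, 24% v 28%: SE0 = 0.0439, SE1 = 0.0438, power 15%.
- p0 = 20%, participants with the sign at baseline removed, 160 per arm, 5% v 10%: SE0 = 0.0295, SE1 = 0.0293, power 40%.

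**5. What a baseline restores.** At p0 = 20%, counting only new cases over all randomised gives 0.80 × 10% = 8% v 0.80 × 5% = 4%: ratio 2.00, difference 4.0 points. Using as denominator only those free of the sign at Visit 1 gives 10% v 5%: ratio 2.00, difference 5.0 points. The numerator rule restores the ratio. The full difference also needs the right denominator.

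**The case against.** The case on the other side has real weight.

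- **The governing definition already says new or worse.** A reader might infer that carried-over damage must count as trial harm. The documents do not support that: section 11's opening sentence and the exclusion item point the other way, and section 4.4 counts from randomisation. What stands against the protocol is one conflicting item and no record with which to apply the rule.
- **Sites have something to compare with.** Every entrant is examined, has a medical history taken, and has a photograph or detailed diagram against which later examinations are to be compared. This is a partial comparator. Its stated purposes are diagnosis and scarring, and nothing requires it to show atrophy or telangiectasia.
- **Only part of the outcome is affected.** Entrants must be symptom-free, so stinging, burning and itching have a baseline in effect. The point is confined to chronic skin signs.
- **Prior exposure and prevalence are not documented.** Section 1.2 describes usual first-line care, not the enrolled cohort, and section 2.6 calls such effects relatively infrequent. The 10% to 30% range is assumed.
- **A difference would not be hidden.** A reader might infer that any difference between strategies disappears. Randomisation balances prior damage in expectation, and the absolute difference falls only from 5.0 to 3.5-4.5 points. The large fall is in a risk ratio that section 10.6 does not plan to report, although readers can form it from the percentages.
- **Unblinded examiners are a separate matter.** Under section 5.1, blinded assessment covers scarring and global severity only. A baseline record would not blind the judgement of whether a sign has worsened.

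Adverse event form details and rules for event onset may sit in the e-CRF or SAP, which are not shown. Neither would replace an examination finding not recorded before randomisation.

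**Conclusion.** The point holds in a limited form. The protocol makes chronic local skin signs a safety outcome, schedules no dedicated baseline record of them, and gives section 11 items that cannot be applied reliably without one. Some carried-over damage may be counted in both arms, raising reported rates and diluting the contrast without favouring either arm in expectation.

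The size depends on a prevalence the documents do not give. The figures above (risk ratio from 2.0 to 1.31-1.10, risk difference from 5.0 to 4.5-3.5 points) rest on the assumed 10% v 5% incidence and on every pre-existing case being recorded. If sites already exclude some of these cases, the ratio is diluted less.

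The comparison would be imprecise even with a baseline: on the same assumptions power is 40% at 20% prevalence. The fix makes the safety result interpretable, not conclusive. The primary outcome and sample size are untouched. The change is worth making because it is cheap and a participant's missing baseline cannot be reliably recovered once she has been randomised.

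**What to change.** 1. At the existing Visit 1 examination, before randomisation, record presence or grade of thinning, wrinkling, striae and telangiectasia, on the same form as at follow-up. Add the item to the Visit 1 list in section 8.1.
2. Mark the baseline cell of the adverse effects row in Table 7.
3. Report these signs as new or worsened since baseline: new signs among participants free of the sign at Visit 1, and worsening by grade among the rest.
4. Reconcile the two section 11 items, so that a local skin sign recorded at Visit 1 that has not worsened is not counted.

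Cost: a short e-CRF checklist at a visit that already takes place, and a few lines of protocol wording. No extra visit or staff are needed. Reported event rates will be lower than under a rule that counts everything seen after dosing, and the report should say why. Participants already randomised without the checklist would have to be handled separately.

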### Treatment acceptability and potential barriers/facilitators to treatment

- Acceptability of treatment strategy at 12 and 24 months using a Likert scale.
- Adherence to treatment at 3, 6, 12, 18 & 24 months.
- Qualitative interview sub-study at 12 months.

### Cost-effectiveness

- Generic utility instrument to measure QoL at 3, 6, 12, 18 & 24 months with EQ-5D-5L (adolescents and adults) and CHU-9 (children).
- Resource use including prescription, direct and indirect healthcare and out-of-pocket costs associated with LS at 3, 6, 12, 18 and 24 months.

Table 3 below lists outcomes according to age bands.

Table 3. Collection methods of outcome measures in age groups

Outcome	Children (5-<12 years)	Adolescents (12-<16 years)	Adults (16 and over)
Flares (number and time to first flare)	Text/email/app every 2 weeks to parent/guardian	Text/email/app every 2 weeks to patient/parent/guardian	Text/email/app every 2 weeks to patient
Progression of scarring	Photographs (at baseline, optional), VASS or clinical examination	Photographs (at baseline, optional), VASS or clinical examination	Photographs (at baseline, optional), VASS or clinical examination
Global clinical severity	Clinical assessment	Clinical assessment	Clinical assessment
Condition specific QoL	CDLQI	CDLQI	VQLI
Generic utility instrument (health related QoL)	CHU-9D	EQ-5D-5L	EQ-5D-5L
Sexual function	-	-	Female Sexual Function Index (FSFI)
Acceptability to treatment	Bespoke questions	Bespoke questions	Bespoke questions
Adherence to treatment	Bespoke questions	Bespoke questions	Bespoke questions
Resource use (bespoke and healthcare)	Bespoke questions	Bespoke questions	Bespoke questions
VIN/vulval SCC	Clinical assessment/medical notes	Clinical assessment/medical notes	Clinical assessment/medical notes
Adverse effects of therapy	Clinical assessment, medical notes/patient/parent/guardian reported	Clinical assessment, medical notes/patient/parent/guardian reported	Clinical assessment, medical notes/patient reported

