### 3.3 Secondary objectives

1. Assess the effectiveness of proactive versus reactive use of TCSs over 24 months in reducing disease progression.
2. Assess the clinical effectiveness of proactive versus reactive strategies for the management of vulval LS for up to 24 months.
3. Assess the safety of using potent and superpotent TCSs in the vulval area over 24 months.
4. Assess the cost-effectiveness of the two treatment strategies.
5. Understand the acceptability of reactive and proactive long-term treatment strategies and the barriers and facilitators to continuing with prescribed treatment.

Trial objectives and outcome measures as mapped in Table 2.

Table 2. Mapped objectives and outcome measures

Objective	Outcome Measure	Outcome Time Point	Method
Primary objective			
Compare the effectiveness of proactive versus reactive strategies for using topical corticosteroids on the number of flares within 12 months, in people aged $\geq 5$ years with vulval Lichen Sclerosis	Number of flares	Over 12 months	Text/app/email reminders every two weeks for 12 months Participant reported
Secondary objectives			
1. Assess the effectiveness of proactive versus reactive use of TCS over 24 months in reducing disease progression	Scarring	At 12 and 24 months	Clinical assessment comparing to baseline photographs, if consent given, or comparing to baseline clinical assessment diagram if consent for photographs not obtained.
	VASS	At 12 and 24 months	Clinical assessment
	Development of VIN or vulval SCC	Over 24 months	Clinical assessment/medical notes
2. Assess the clinical effectiveness of proactive versus reactive strategies for the management of vulval Lichen Sclerosis for up to 24 months	Global clinical severity assessment	At 3, 6, 12, 18 and 24 months	Clinical assessment
	Sexual function	At 12 and 24 months	Participant reported
	Time to first flare	At 1 st flare over 12 months	Text/app/email reminders every two weeks for 12 months Participant reported

Objective	Outcome Measure	Outcome Time Point	Method
	Condition specific QoL CDLQI (adolescents and children) and VQLI (adults)	At 3, 6, 12, 18 and 24 months	Questionnaire Participant reported
	Generic utility instrument measured by EQ-5D-5L (adolescents and adults) and CHU-9 (children)	At 3, 6, 12, 18 and 24 months	Questionnaire Participant reported

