### 5.1 Maintenance of randomisation codes and procedures for breaking code

The research staff randomising a participant won't be blinded to the allocation due to the nature of the treatment.

The outcomes to which an assessor will be blinded to treatment allocation will be scarring, assessed at 12 and 24 months. Global clinical severity will normally be reported by the site unblinded clinician at all time points but additionally it will be assessed by the blinded assessor at 12 and 24 months. The blinded assessor will be someone that is deemed by the PI as adequately qualified (and recorded on the delegation log) to examine and identify changes in participants with vulval LS. They will not be involved in any other trial activities. A blinded assessor will compare changes at 12 and 24 months against baseline photos or clinical assessment diagram. Where a blinded assessor is not available at the time of clinical assessment, assessment will be made subsequently by review either of the photos taken during the assessment or by comparison with the clinical diagram, and record findings. Revealing the treatment strategy allocation to the assessor should not be necessary as both involve topical steroids. However, in the unlikely scenario that assessors identify safety concerns, such as vulval cancer/pre-cancer, they will report to the site Principal Investigator (PI), who is unblinded, and who will inform NCTU as per the NCTU standard process.

The trial statisticians and Trial Steering Committee (TSC) members will be blinded to participant group allocations. An unblinded independent NCTU statistician will produce closed reports for the Data Monitoring Committee (DMC). No emergency unblinding processes are necessary. The Table 4 below describes which trial staff will be blinded/unblinded to the treatment allocation.

Table 4. Blinding status of the PEARLS trial staff

	Blinding status	Comments
Participant	Not blinded	Not practical due to trial design
Principal Investigator and other site staff	Not blinded	Not practical due to trial design
Clinical assessor at site	Blinded assessor	Scarring and global clinical severity assessment at 12 and 24 months
	Unblinded assessor	Global clinical severity at all time points and development of VIN or vulval SCC at 24 months
Chief Investigator	Blinded	The Chief Investigator will remain blinded to treatment allocation with an exception of participants recruited at their site.

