#### 7.4.2 Exclusion criteria

1. Previous vulval intraepithelial neoplasia (VIN) or vulval squamous cell carcinoma (SCC)
2. Contraindications to topical steroids
3. Concomitant use of other topical anti-inflammatory vulval treatments
4. Using systemic immunosuppressants (for any indication)
5. Using systemic treatment for LS
6. Patients with surgical alteration of vulval skin as part of gender reaffirming surgery, or patients not born with a vulva
7. Pregnant and breastfeeding women

The trial inclusion criteria are designed to mimic usual practice. LS is a clinical diagnosis and biopsy is only performed if there is a poor response to first-line treatment, diagnostic doubt or concern of pre-malignancy/malignancy. Those patients who are asymptomatic and with minimal evidence of active disease at baseline are considered to be well-controlled. Girls aged 5 or older will be included as there is paucity of evidence for LS management in paediatric patients.

By definition, anyone with previous vulval intraepithelial neoplasia, or vulval cancer, have complicated LS, are not eligible for the trial. If there is sensitivity to topical corticosteroids entering the trial might worsen this. Finally, other anti-inflammatory agents, topical or systemic, would act as a confounder, and patients on these treatments are more likely to have complicated disease.

In accordance with the Clinical Trial Facilitation Group "recommendations related to contraception and pregnancy testing in trials", given that the trial IMPs are all licensed products, participants of child-bearing potential can be included in the trial providing an acceptable effective method of contraception is used until treatment discontinuation. Acceptable contraceptive methods include: established use of oral, injected or implanted hormonal methods; placement of an intrauterine device (IUD) or intrauterine system (IUS); condom or occlusive cap (diaphragm or cervical/vault caps) with spermicide; true abstinence (when this is in line with the preferred and usual lifestyle of the participant); or vasectomised partner. Participants will be advised of the importance of these requirements before entry into the trial. The trial IMPs are licensed products which are routinely prescribed to pregnant women therefore a pregnancy test will not be required before entry to the trial, but the participant should contact their GP and seek further direction if pregnancy should subsequently be confirmed.

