### 10.6 Assessment of safety

Analysis of safety data will be presented descriptively using frequency counts and percentages in each allocated group.

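### VIN/vulval SCC has no pathology-confirmed event definition, and it is classed both as effectiveness and as safety, so its analysis rule and analysis set are unsettled

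*Protocol*

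**What the plan says.** **Source and assessor.** Table 2 (section 3.3) and Table 3 (section 4.4) give the method as "Clinical assessment/medical notes". Table 7 (section 8.7) names the clinician as source and marks the 24-month visit only. Table 4 (section 5.1) lists among the unblinded assessor's tasks "Global clinical severity at all time points and development of VIN or vulval SCC at 24 months". Blinded assessment is planned for scarring and, at 12 and 24 months, for global severity.

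**Biopsy in usual care.** Section 7.4.2 says that "biopsy is only performed if there is a poor response to first-line treatment, diagnostic doubt or concern of pre-malignancy/malignancy". Section 11.5 sends suspected vulval cancer or pre-cancer to the site's usual investigation of suspected malignancy.

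**Classification.** In Table 2, "Development of VIN or vulval SCC" stands under the objective "Assess the effectiveness of proactive versus reactive use of TCS over 24 months in reducing disease progression", with the time point given as over 24 months. The synopsis and section 4.4 list under Safety "Development of vulval intraepithelial neoplasia or vulval squamous cell carcinoma at 24 months". Section 11.4 makes pre-cancerous change a targeted adverse event.

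**Analysis.** Section 10.2 gives secondary outcomes an adjusted regression model or a non-parametric estimator. Section 10.6 says "Analysis of safety data will be presented descriptively using frequency counts and percentages in each allocated group". Under section 10.8, secondary outcomes are analysed by allocation. Safety outcomes are restricted to randomised participants with at least one dose and analysed both by treatment received and by allocation. Neither 10.2 nor 10.6 names VIN/SCC.

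**The concern.** There are two separate weaknesses.

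First, the tables do not say what counts as an event. As written, either a clinical judgement or an entry in the notes suffices, and the judgement is made by someone who knows the allocation. The protocol does separate clinical from histological diagnosis for lichen sclerosus itself (Definitions), and plans to record which applied. It makes no such distinction for its pre-malignant and malignant outcome. What counts as an event decides what the e-CRF collects, so it has to be settled before data accrue. The SAP need only be agreed before database lock.

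Second, the two classifications lead to different forms of comparison and different denominators, and no text says which governs. The denominators differ in a way related to arm: a reactive participant uses the steroid only during a flare (Table 6), so one who never flares may never take a dose and would leave the safety set. A proactive participant with the same quiet course is dosed twice weekly and stays in.

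Reducing cancer risk is a named treatment goal (section 1.2), and readers will look at this comparison however few the events.

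**Working it through.** **The two classifications side by side**

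| | Table 2 reading | Synopsis and 4.4 reading |
|---|---|---|
| Class | Effectiveness, objective 1 | Safety |
| Time | Over 24 months | At 24 months |
| Method | 10.2: adjusted model or non-parametric estimator | 10.6: counts and percentages |
| Set (10.8) | By allocation; no dose condition in that sentence | At least one dose; by treatment received and by allocation |

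**Check of the inputs.** The protocol states no figure for VIN/SCC. The flare rate and dispersion used below are those of its sample size (section 10.1): rates 4 and 3 a year, dispersion k = 0.34, 90% power, two-sided 0.05.

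- Variance term: V = 1/4 + 1/3 + 2 × 0.34 = 1.263.
- n per arm = (1.960 + 1.282)² × V / (ln 0.75)² = 10.51 × 1.263 / 0.0828 = 160.4, or 322 in total.
- With the null variance taken at the mean rate, n = 159.5 per arm, or 320 in total. This is the stated figure.
- 320 / 0.80 = 400. The stated numbers reproduce, and this point does not change them.

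**Reactive participants who never flare.** For a negative binomial count with mean m and dispersion k, P(0) = (1 + k·m)^(−1/k).

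- 12 months, m = 4: (1 + 1.36)^(−2.94) = 0.080, or 16 of 200.
- 24 months, m = 8, if each participant's rate persists: (1 + 2.72)^(−2.94) = 0.021, or about 4 of 200.
- Sensitivity: the quoted mean and SD of 4.0 and 2.8 give a moment dispersion of (2.8² − 4)/4² = 0.24. P(0) is then 1.96^(−4.17) = 0.061 at 12 months and 2.92^(−4.17) = 0.012 at 24 months, or about 12 and 2 of 200.

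**Expected events.** The protocol gives only a relative rate for SCC (section 1.1), so the 24-month risk is an assumption. Expected events are 400 × risk. Power is for a doubling of the risk with 200 per arm.

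| Assumed risk | Events in 400 | Power |
|---|---|---|
| 0.25% | 1 | 6% |
| 0.5% | 2 | 8% |
| 1% | 4 | 13% |
| 2% | 8 | 22% |
| 3% | 12 | 30% |

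With 200 per arm, a split of 5 against 0 gives Fisher p = 0.061, and 6 against 0 gives p = 0.030. With so few events, an adjusted regression under 10.2 would probably not be estimable.

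**The case against.** **Suspected cases will be biopsied anyway.** This largely stands. Sections 7.4.2 and 11.5 point to biopsy or investigation on suspicion, and the medical notes, where a pathology report would sit, are a named source. A reader might infer that VIN/SCC will be scored without histology; the documents show only that histology is not required.

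**Suspicion and diagnosis are already distinct.** This stands. Section 11.5 lists suspicion as its own event, while the outcome is development of disease. Section 11.5 should not be read as merging the two.

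**Detection does not rest on unblinded eyes alone.** This stands in part. Under section 5.1, blinded assessors who see possible cancer or pre-cancer report it to the site investigator, who is unblinded.

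**Histology does not cure detection bias.** This stands. It removes unconfirmed calls. The unblinded clinician still sets the threshold for biopsy. The documents give no ground for presuming which arm that would favour.

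**The two rules can coexist.** This stands in part. Safety is a subheading within the secondary outcomes, counts and a model are compatible, and both classes include an analysis by allocation. A reader might infer two mutually exclusive rules. What the documents show is one outcome in two classes, with no statement of which dose condition or which comparison is the main one.

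**This is SAP detail.** The choice of estimator is. The contradiction between Table 2 and section 4.4, and the definition of a countable event, belong to the protocol.

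**Conclusion.** The point holds in a limited form. The protocol allows an unblinded clinician to score VIN or vulval SCC without confirmation, and it leaves open which analysis rule and set govern the outcome.

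The size is modest. The dose condition could remove about 8% of the reactive arm at 12 months and about 2% at 24 months, with 6% and 1% under the lower dispersion. These figures assume that the survey rate applies to the reactive arm, that a participant without a flare takes no dose, and, for 24 months, that individual rates persist. About 4 missing reactive participants hardly move a percentage, but the exclusion depends on disease course in one arm only and is easily avoided.

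The event count of 1 to 12 rests wholly on the assumed risks. A reader might infer that one or two unconfirmed calls would decide the comparison. The documents do not support that: no rate is given, the outcome is not powered, and even 5 against 0 would not reach p < 0.05. An unconfirmed call would colour a descriptive table. The primary result is unaffected.

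**What to change.** 1. In Tables 2, 3, 4 and 7, define the counted event as VIN or vulval SCC confirmed on the routine pathology report, dated by that report, at any time over 24 months. Use that time frame throughout in place of the present mix of over and at 24 months.
2. Add a pathology-confirmed yes/no field to the e-CRF.
3. Report suspected but unconfirmed cases separately, by arm.
4. Classify the outcome once. Make all randomised participants by allocated arm the main comparison, as counts with an exact confidence interval for the difference. Keep the treatment-received table of section 10.8 as supplementary.
5. State that confirmation removes unconfirmed calls but not bias from an unblinded threshold for biopsy, and that the comparison is descriptive because events will be few.

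The cost is wording in four tables, matching text in the synopsis and sections 4.4, 10.6 and 10.8, and one e-CRF field. It uses pathology that usual care already produces and sets no rule on when to biopsy. The downside is that a suspected case that is never biopsied does not enter the main comparison; step 3 keeps it visible.
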